5.	Ethical considerations	.34

1. Executive Summary

The main objectives of CESTA are (1) to compare the efficacy of two cervical cancer screening algorithms: HPV test followed by visual inspection with acetic acid (VIA) and treatment (HPV + VIA + treat) and HPV test followed by immediate treatment (HPV + treat). The study will be conducted to address its objectives in women living with HIV (from now on called HIV positive women) and HIV negative women; (2) to compare the cervical intraepithelial neoplasia grade 2 or 3 (CIN2/3) cure rates of treatment with cryotherapy and thermal ablation (TA) 12 months after the treatment in HIV positive women; and 3) to model the comparative cost-effectiveness of the two screening and treatment strategies described in (1) and the 2 treatment methods described in (2).

The study will be carried out through 2 modules as the study outlines differ considerably for the Algorithms objective (Obj 1) and the cure rate objective (Obj 2). The cost-effectiveness study (Obj 3) will be carried out in both modules with the epidemiological comparisons aligned with the respective modules.

Module 1 will study the main objectives 1 and 3 among 3,000 HIV positive women in South Africa and 7,500 HIV negative women in Senegal.

HIV positive women will be recruited from HIV care clinics, also called antiretrovirals (ARV) clinics in the Durban area, South Africa. After giving informed consent, women will be screened with HPV testing and those that are HPV positive will be randomized at a 4:1 ratio into HPV + VIA + treat (Arm 1) and HPV + treat (Arm 2) in 1 of the 2 CESTA study clinics. Women in Arm 1 will receive VIA and only positive for VIA will be treated. In Arm 2, all HPV positive women will be treated. Women that are eligible for ablative treatment will be randomized into treatment with TA or cryotherapy in both arms. Others will be referred to colposcopy. After VIA in Arm 1 or before treatment in Arm 2, the nurses will collect 2-4 biopsies on all HPV positive women. The biopsies will be used as gold standard for disease detection. The first 200 women treated will be followed up intensely for 4 weeks to assess side-effects and levels of HIV shedding. Subsequently treated women will be called by telephone after 1 week and 1 month to assess side-effects and satisfaction with the procedures. Smartphone enhanced VIA (SEVIA) with patient navigation will be used in 1 of the 2 study clinics. 2-3 Pictures are taken with the SEVIA smartphone tool after application of acetic acid to the cervix. The pictures are sent in a secure way to expert reviewers who provide feed-back to the nurse in real time. The application can also be used to track adherence of the

women to the screen and treat procedures or referral and send automated reminders of appointments. Outcomes on performance of VIA and patient adherence will be compared between study clinic that uses SEVIA and the one not using SEVIA. All women who were HPVpositive or were treated will be called back after 1 year for a follow-up visit. Women will be screened with HPV testing and VIA and 2-4 colposcopy-directed biopsies will be taken from all HPV positive women. Women with remaining/recurrent CIN2+ disease will receive appropriate management.

HIV negative women will be recruited from the communities in the Dakar area. They will be screened in 1 of 4 CESTA study clinics. Procedures will be similar as in HIV positive women, except that the randomization rate will be 3:1 for Arm 1 and Arm 2 and that the women eligible for ablative treatment will be all treated with TA. SEVIA will be applied in 2 of the 4 study clinics to compare SEVIA outcomes in those clinics using it or not. Follow-up of treatment side-effects and women's satisfaction will be by telephone after 1 week and after 1 month. Similar to HIV positive women, all HPV positive women or those treated will be invited for a 1-year follow-up visit with the same procedures as described above.

The cost-effectiveness study will answer questions on the comparative value and efficiency of the two screening arms and two treatments respectively, using epidemiological data collected through the clinical study for the effectiveness portion of the analysis. Cost data collected through questions embedded in the clinical questionnaires and by more in-depth but limited interview will be supplemented by administrative data where necessary to form the cost portion of the analysis. The study will use a well-validated cervical cancer model.

Module 2 will study the main objectives 2 and 3 among 920 HIV positive women with CIN2/3 in South Africa. An estimated 143 women will have CIN 2/3 on biopsy from Module 1 and can be directed to participate in Module 2. A remaining 777 women with CIN2/3 will need to be recruited through 8-9 ARV clinics. Since 2018, women are screened routinely with liquid based cytology (LBC) in South Africa. We will invite women with LBC results of low-grade squamous intraepithelial lesions or worse (LSIL+) to participate in the CESTA Module 2 study in 1 of the 2 CESTA study clinics dedicated to Module 2. After giving informed consent, 2-4 cervical biopsies will be taken by the study nurses. Women with biopsy results <CIN2 will be referred back to the ARV clinic for routine cervical cancer screening. Women with CIN2/3 and that are eligible for ablative treatment will be randomized into TA and cryotherapy. Others will be referred to

colposcopy for appropriate management. Similar to Module 1, women will be called by telephone after 1 week and 1 month to assess side-effects and satisfaction with the treatment. All women who were CIN2/3 and were randomized to ablative treatment or referred to colposcopy will be invited for a 1 year and 2 year follow-up visit. Similar as in Module 1, Women will be screened with HPV testing and VIA and 2-4 colposcopy-directed biopsies will be taken from all HPV positive women. Women with remaining/recurrent CIN2+ disease will receive appropriate management.

The cost-effectiveness study will assess the comparative value and efficiency of the two treatment methods.

2. Background

2.1. Clinical need

Cervical cancer remains a serious public health problem, with more than 500,000 new cases and 300,000 deaths occurring every year, particularly in developing countries where 87% of cases occur. Although rates of cervical cancer vary considerably, cervical cancer ranks first or second in all individual sub-Saharan countries, while it is the leading cause of cancer deaths at 56,444 cases per year [1] in the subcontinent. Cytology based cervical cancer screening programs have successfully reduced cervical cancer incidence in developed countries but, with few exceptions, not in low- and middle income countries (LMIC). Programs using cervical cytology, which detects cellular changes indicating cervical intraepithelial neoplasia or cancer, are very complex to implement properly and the method has limited sensitivity and low reproducibility, which imposes the need for repeating tests frequently. This results in high cost and logistic complications which hamper the implementation and success of cytology-based screening programs in LMIC. Alternative screening methods have been developed, the two most studied being testing for human papillomavirus (HPV) and visual inspection with acetic acid (VIA). VIA can be implemented at low cost and allows for an immediate result to be given to the patient. This can be followed by a treatment at the same visit. However, VIA is operator dependent, lacks reliable means of quality assurance control, has a low positive predictive value and results in overtreatment of large numbers of women [2].

It is now clear that a group of 13 human papillomavirus (HPV) types are the causal agents of cervical cancer and that HPV 16 and 18 are responsible for about 70% of all cervical cancer.

HPV is a very common infection usually acquired shortly after initiation of sexual activity, but most infections are cleared by the immune system within 2 years after acquisition and only a few persist and progress to cancer.

The recently introduced HPV vaccine has the potential to prevent 70% of cervical cancers, and a newer version has the promise to offer even more protection against cervical cancer. Vaccination needs to take place before the beginning of sexual activity, the target age recommended by the WHO for vaccination being 9-14 years old [3]. The protective effect on cervical cancer incidence, however, will only be noted several decades later, as the peak of cervical cancer incidence is in women in their mid-forties. Even in the most optimistic scenario where vaccination coverage in the target age group would reach 100% within the 10 coming years in all countries of the world, based on Globocan data we estimate that nearly 28 million women will still be affected by cervical cancer in the coming 40 years [1].

Therefore cervical cancer screening programs remain a high priority for most countries but especially for developing countries, where most cervical cancer cases occur.

In 2014 WHO updated its evidence-based recommendations for comprehensive cervical cancer control including vaccination, screening, treatment and palliative care [WHO 2014]. An important gap in the evidence, emphasized by the international expert panel, was the lack of clinical data directly comparing screening by HPV testing with or without VIA triage testing in HIV negative as well as HIV positive women. Notably data on the benefits, side-effects and cost-effectiveness of the screen and treat algorithms using these tests were lacking [4]. This lack of evidence results in recommendations on the use of algorithms without indications on what would be the most cost-effective approach in which conditions.

Therefore, the 2 screen and treat algorithms of interest that need to be carefully compared and evaluated in order for WHO to provide strong recommendations to low- and middleincome countries (LMIC) are: (1) Screening by HPV test followed by VIA for triage of HPV positive women and; (2) Screening by HPV test alone; each followed by ablative treatment of screen-positives. We will also compare two ablative treatment methods for cervical precancer: cryotherapy and the novel thermal ablation. WHO has recently recommended that TA or cryotherapy can be used to treat eligible cervical legions, however these recommendation were based on weak evidence in HIV negative women and non-existent evidence for HIV positive women.

Each of the aims will be evaluated in different modules: Mod 1, a randomised controlled trial (RCT) to compare the efficacy of the two screen-and-treat algorithms, and Module 2, another

RCT to compare the 12 and 24 months CIN2+ cure rates of each ablative treatment. The first module will be carried out among HIV positive and HIV negative women in South Africa and Senegal, respectively. The comparison will be based on HPV positive women with histological high grade squamous intraepithelial lesions or worse (HSIL+) adequately treated, those left untreated and those who were treated and did not have confirmed disease (overtreatment) randomized to each algorithm.

The second module will be carried out in HIV positive women with histologically diagnosed CIN2/3 at the time of randomization. The third aim on cost-effectiveness will be evaluated within each module to provide a complete picture on cervical cancer screening strategies in the context of the cervical cancer elimination initiative.

2.2. HPV and cervical cancer in HIV-positive women

Most healthy women clear HPV infection on their own, while clearance in women with human immunodeficiency virus (HIV) is more limited, and women with HIV are more likely to experience progressive cervical changes [5]. Studies suggest that HIV-infected women were respectively 1.8, 2.1 and 2.7 times more likely to display high, intermediate and low risk HPV infections in the cervix than HIV uninfected women [5, 6]. Thus, HIV-positive women have higher rates of HPV persistence and progression to invasive cancer when compared to HIV-negative women and in sub-Saharan Africa, HIV-infected women are 6 times more likely than HIV uninfected women to develop cervical cancer [7].

The effect of antiretroviral therapy (ART) on cervical cancer precursor lesions (CIN2+) was evaluated in a recent meta-analysis. It was found that women living with HIV on ART have a lower prevalence of both high-risk HPV and CIN2+ lesions, compared to HIV positive women not on ART. Furthermore, a reduction in the incidence and progression of CIN2+ lesions was seen in women on ART, and an increase in regression of CIN2+ lesions. Notably, these effects remained after adjusting for immune restoration indicators such as CD4 cell count and duration of ART use [8].

HIV positive women typically have more remaining/recurrent disease after treatment of precancerous lesions. These will be discussed in the sections of the respective treatments.

2.3. HPV testing in cervical screening

Practically every invasive cancer and the vast majority of CIN 2/3 express high-risk (hr) HPV [9]. Currently, there are several laboratory tests for detection of cervical HPV infection which have high sensitivity and are highly reproducible. These tests are recommended by WHO and considered to replace cervical cytology for primary screening. More and more countries are introducing HPV tests in their programme. They are highly sensitive to detect cervical cancer precursors (sensitivity typically >90%), highly reproducible, and have the capacity to detect more disease at an earlier stage [10]. In addition, HPV testing has a high negative predictive value that allows extension of the screening interval, with consequent savings that can compensate the possibly higher cost of the test compared to cytology or VIA. An additional advantage of HPV testing is the possibility to use vaginal specimens that are self-sampled by the woman. It has already been shown that this approach can increase the coverage of a screening program [11]. Recently, several HPV tests have been developed that are technically easier to implement and provide results more rapidly, compared to the conventional HPV tests. Two of those tests, the careHPV test (Qiagen) and HPV GeneXpert test (Cepheid) were recently prequalified by the WHO in-vitro diagnostics group, which would make procurement easier for middle and low income countries.

Screening with HPV has the problem that transient HPV infections are very common, particularly among young women, where the majority of infections will regress spontaneously. Even among women over 30 years of age, HPV infection still tends to regress and only in a fraction of cases with persistent infection, it can lead to true cancer precursors and cervical cancer. Thus, one of the main issues to resolve is how to triage HPV positive results, i.e. to identify, for further evaluation and treatment, those HPV-positive women who are most likely to have or to develop in the near future significant disease that requires treatment. Direct treatment of HPV-positive women results in overtreatment, as the positive predictive value of HPV testing is around 15%. In general, a degree of overtreatment with cryotherapy is accepted because the treatment is safe with no adverse effects, well tolerated and serious side effects such as cervical stenosis are extremely rare [12]. In addition, ablation treatment of the cervix may have a prophylactic effect on future infections with HPV. Recent work has also shown that the junction between the ecto- and endocervix harbours embryonic reserve cells that have the potential to transform into neoplastic cells when infected with oncogenic HPV, and that their destruction may be protective of future cervical neoplastic developments [13]. In high-income

countries (HIC), triage of HPV positive women is usually done by cytology. In LMIC, where it is challenging to implement good quality cytology, triaging by visual inspection with acetic acid (VIA) is recommended, as well as no triage approach [4]. One of the major concerns is that the addition of VIA which has a known limited sensitivity may jeopardize the overall performance of both tests combined.

2.4. VIA testing in cervical screening

VIA is a technique in which cervical neoplastic lesions are visually diagnosed after application of 3-5% acetic acid without using any magnification device. The examination can be performed by any trained health worker, mostly nurses. The training in VIA is still not standardized and especially supervision after initial training is very difficult to organize. Therefore the technique remains subjective as it is based on the interpretation of what is seen by the health care provider after application of the acetic acid on the cervix. As a result, the reported test characteristics of VIA vary greatly. One recent multi-country study in Nicaragua, Uganda and two sites in India, reported sensitivity between 22% in one site in India and 74% in Uganda with specificity of 95% and 67%, respectively, and associated positivity rate of 6% and 34%, respectively [14]. One advantage of the technique is that it allows a single-visit approach in which women are screened and treated with ablative treatment (cryotherapy or thermal ablation) at the same clinic visit.

In case of a screen and treat algorithm that does not involve VIA (e.g. HPV testing), a variant of VIA is applied before ablative treatment, in order to assess that the woman does not have any condition that would make her ineligible for ablative treatment, such as a lesion or squamo-columnar junction (SCJ) that reaches endocervically, an apparent lesion that covers >75% of the ectocervix, and suspicion of invasive cancer. All other cases are amenable for treatment, even without visible lesion.

2.5. Treatment of pre-cancerous lesions

Recent WHO guidelines recommend ablation by cryotherapy or thermal ablation, and excision by large loop excision of the transformation zone procedure (LLETZ, also called LEEP) as different forms of out-patient surgical treatment of CIN2/3.

2.5.1. Cryotherapy

Cryotherapy consists of freezing the lesion and underlying tissue to a temperature of at least -20° Celsius. The treated tissue necrotises and is replaced by new healthy epithelium. A reusable probe is applied to the cervix and the freezing is obtained through decompression of either carbon dioxide (CO2) or nitrous oxide (N2O) gas. The main side-effect is a watery vaginal discharge for up to 2-3 weeks, which is generally well tolerated. The equipment is simple, no electricity is needed and the technique is relatively easy to perform. Cryotherapy can be provided by a variety of healthcare personnel including general doctors, nurses, midwives and auxiliary health workers who can be trained in short sessions. For those reasons, cryotherapy is very suited for LMIC. In addition, it can also be used in a single visit screen-and-treat approach in combination with a screening test that provides immediate results, such as VIA. One potential impediment of the technique is the inadequate availability or elevated cost of the freezing gas. Lesions that are not eligible for cryotherapy are those that reach >2mm in the endocervical canal; are larger than the cryoprobe; cover more than 75% of the ectocervix; and should be treated with LLETZ. Lesions that are suspicious of invasive cancer should be biopsied and treated according to diagnostic work up.

A meta-analysis showed that cryotherapy is 92% and 85% effective to eliminate CIN2 and CIN3, respectively (cure : normal cytology at follow-up) [15].

In a recent meta-analysis of studies reporting cryotherapy and LLETZ in HIV positive and HIV negative women, Debeaudrap P. *et al.* observed that residual or recurrent high-grade lesions were detected in 21.6% of women treated with cryotherapy, compared to 12.6% after LLETZ among HIV-positive women treated for CIN2+/HSIL+ [16]. These patients were twice as likely to suffer from treatment failure compared to HIV-uninfected women. The authors mentioned that there were no studies reporting on cure rates of thermal ablation in HIV positive women fitting the inclusion criteria of the meta-analysis. Greene S. *et al.* recently reported a RCT among 400 HIV-infected women with cervical intraepithelial neoplasia CIN 2/3 disease that were randomized to receive cryotherapy or LLETZ. At 12-months, more women treated with cryotherapy experienced recurrent HSIL than those who underwent LEEP (27% vs 18%; P=0.031). At 24 months, HSIL increased in both arms and remained significantly higher in the cryotherapy arm (37% vs 26%; P=0.018). Overall, the rate of recurrence of HSIL+ was 21.1 per 100 woman-years after cryotherapy and 14.0 per 100 woman-years after LLETZ [Greene S. *et al.* Cryotherapy versus loop electrosurgical excision procedure among HIV-infected women (JAMA (in press)).

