Women with CIN2+ on biopsy who have not been treated based on screening results from arm 1 will also be randomised to sub-arms A and B if eligible for ablative treatment or referred to colposcopy otherwise.

ARM 2:

Study procedures in this arm are mostly similar to Arm 1. A nurse will carry out a speculum examination and collect an endocervical swab to measure HIV shedding. She will then perform a visual assessment for treatment using acetic acid (VAT, see section 2.4) to assess if the patient is eligible for ablative treatment and in half of the study clinics, 2-3 pictures will be taken with the SEVIA App. After VAT, 2-4 biopsies will be collected at the SCJ from all quadrants that show aceto-white changes or at 12 and 6 'o clock if no acetowhite changes are visible.

All women that are eligible for ablative treatment will be treated and randomised into subarm A (cryotherapy) and sub-arm B (thermal ablation) as in Arm 1; women with VAT not eligible for ablative treatment will be referred to the colposcopy clinic for appropriate referral and management.

Similar as for VIA, the VAT examination is inadequate if the SCJ is not entirely visible. In this case, an endocervical brush will be collected for cytological examination and the woman will be referred to colposcopy once the cytology result is known.

In both arms, endocervical sample collection for HIV shedding will be done after 1, 2, 3, and 4 weeks in 100 women (each arm) who received treatment (modes of selection for these women still needs to be decided). At those respective visits, women will answer a questionnaire on perceived side-effects and acceptability of treatment. Women who do not come back for HIV shedding sample collection will be called by telephone after 1 week and 1 month to assess perceived side-effects and acceptability of treatment. The nurse will take the necessary actions if serious side-effects are reported.

In addition, all treated women will be recalled at 12 months for a follow-up visit including HPV testing, VIA with colposcopy and biopsy on HPV positive women, and those with CIN2+ will be treated as appropriate.

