Women with LSIL+ will attend the closest CESTA study clinic. After informed giving written informed consent, the nurse will take some short questionnaires on demographics and sexual history, and socio-economic characteristics. A health economics questionnaire focused on

participant travel time and expenditures will also be administered. The nurse will collect 2-4 biopsies, with the same procedure as described under Module 1 (section 3.2.1.). Women will then receive an appointment for an additional biopsy results visit. At that visit, all women with CIN2 or 3 without glandular lesions and eligible for ablative treatment through VAT will be randomized in a 1:1 ratio into cryotherapy and thermal ablation, performed by the nurse at the same visit after taking 2-3 pictures with the SEVIA application. Ablation ineligible women will be referred to colposcopy and will be managed and treated appropriately including LLETZ. Women with normal or CIN1 biopsy results will be exited from the study and referred back to the ARV clinic to follow the South Africa standard care recommendations, i.e. rescreening after 1 year.

The VAT examination is inadequate if the SCJ is not completely seen and in that case, the nurse will obtain an endocervical brush for cytology and the women will be sent to the colposcopist when the cytology results are available.

Similarly as in Module 1 (section 3.2.1), women who receive treatment will be called by telephone 1 and 4 weeks after treatment and answer a questionnaire on perceived side-effects and acceptability of treatment. The nurse will take the necessary actions if serious side-effects are reported.

In addition, all treated women will be recalled at 12 and 24 months for a follow-up visit including HPV testing, VIA, colposcopy and biopsy on all HPV positive women, and those with CIN2+ will be treated as appropriate. The SEVIA application will also be used for quality control of the VAT by the nurse, and for patient navigation, as described in Module 1.

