3.9. Statistical methods Module 2 Cure rate study

For primary objective 1, we will compare the CIN2/3 cure rates of treatment with cryotherapy (Arm A) or thermal ablation (Arm B) after 12 months of treatment among HIV positive women using Z-test for comparison of proportions in intention-to-treat and per-protocol analyses.

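### Sections 2.4 and 2.5.1 set different eligibility limits, so a woman can pass the gate to the cryotherapy/thermal ablation randomisation and be ineligible in the cryotherapy arm only

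*Protocol*

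**What the plan says.** **Gate to randomisation.** In Module 2 (section 3.8), women with CIN2/3 and no glandular lesion who are "eligible for ablative treatment through VAT will be randomized in a 1:1 ratio into cryotherapy and thermal ablation". Women found ineligible for ablation go to colposcopy and may receive LLETZ. In the South African part of Module 1 (section 3.2.1), women eligible for ablation are likewise randomised to sub-arm A (cryotherapy) or B (TA).

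**What the gate checks.** Section 3.2.1 describes a "visual assessment for treatment using acetic acid (VAT, see section 2.4) to assess if the patient is eligible for ablative treatment". Section 2.4 names a lesion or squamo-columnar junction that extends endocervically, "an apparent lesion that covers >75% of the ectocervix, and suspicion of invasive cancer". It then closes: "All other cases are amenable for treatment, even without visible lesion".

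**What section 2.5.1 says about cryotherapy.** "Lesions that are not eligible for cryotherapy are those that reach >2mm in the endocervical canal; are larger than the cryoprobe"; the list goes on to those that "cover more than 75% of the ectocervix; and should be treated with LLETZ". Probe size is listed separately from the 75% limit, so it is an additional criterion.

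**What section 2.5.2 says about TA.** It allows more than one application of the probe and states no lesion-size limit.

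**Analysis.** Section 3.9 compares 12-month cure rates "using Z-test for comparison of proportions in intention-to-treat and per-protocol analyses".

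**The concern.** The gate comes before allocation, but one of the two methods carries a further exclusion that the gate does not name. A woman whose lesion is wider than the cryoprobe yet covers no more than 75% of the ectocervix meets section 2.4 and can be randomised. Under section 2.5.1 she is ineligible if the card says cryotherapy. Nothing comparable is stated if the card says TA.

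The protocol does not say what happens to her. If section 2.5.1 is applied at the point of treatment, the exclusion falls after allocation, in one arm, and selects on lesion size. This has two consequences:

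- **Intention-to-treat:** the randomised groups stay intact, but the cryotherapy arm contains women treated by LLETZ. The result is no longer a clean contrast of the two ablative methods.
- **Per-protocol:** if diverted women are dropped, large lesions leave the cryotherapy arm and stay in the TA arm. That is selection bias if such lesions are harder to cure.

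Both effects can favour cryotherapy, so agreement between the two planned analyses would not by itself rule the problem out.

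**Working it through.** **1. Texts side by side**

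| Criterion | Section 2.4 (VAT, before allocation) | Section 2.5.1 (cryotherapy) | Section 2.5.2 (TA) |
|---|---|---|---|
| Endocervical extension | Any | More than 2 mm | None stated |
| Share of ectocervix | Over 75% | Over 75% | None stated |
| Larger than the probe | Not named | Ineligible | None stated |
| Suspected cancer | Ineligible | Biopsy and work-up | None stated |

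The endocervical limits also differ, but there section 2.4 is the stricter text, so the difference opens no one-sided exclusion after allocation. Only the probe-size row does.

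**2. The plan's own figure.** Section 3.9.1 assumes 70% against 80% cure, 80% power and two-sided 0.05. With pooled variance and no continuity correction, n per arm = [1.96·√(2·0.75·0.25) + 0.8416·√(0.7·0.3 + 0.8·0.2)]² / 0.10² = 293.2, rounded up to 294. That is 588 in total (Table 6: 589). Then 589/0.8 = 736 for attrition and 736/0.8 = 920 for ineligibility, so the stated 920 reproduces. Power at 589/2 = 294.5 evaluable per arm is 80.2%.

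**3. Unknown input.** Let f be the share of randomised women whose lesion exceeds the cryoprobe but meets section 2.4. The documents do not give f. The range 2-20% is an assumption.

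**4. Intention-to-treat, if these women receive LLETZ in the cryotherapy arm.** Shift = f × (LLETZ cure − cryotherapy cure). The only comparative figure in the protocol is the trial in HIV-positive women cited in section 2.5.1, where at 12 months "more women treated with cryotherapy experienced recurrent HSIL than those who underwent LEEP (27% vs 18%; P=0.031"), a difference of 27 − 18 = 9 points. Applying it to large lesions is an assumption. Power is for true cure of 70% with cryotherapy and 80% with TA.

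| f | Shift = f × 9 | Cryotherapy arm | Power |
|---|---|---|---|
| 2% | 0.2 points | 70.2% | 79% |
| 10% | 0.9 points | 70.9% | 73% |
| 20% | 1.8 points | 71.8% | 64% |

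**5. Per-protocol, if these women are dropped from cryotherapy only.** Assume no true difference, 75% overall cure with either method, and large lesions g points harder to cure. If cure in the other lesions is c, then c − f·g = 75%. Cryotherapy shows c and TA shows 75%, so the spurious difference is f × g. With d = f·g and SE = √[0.75·0.25·(1/(294.5(1−f)) + 1/294.5)], the two-sided error is Φ(d/SE − 1.96) + Φ(−d/SE − 1.96).

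| f | Spurious difference, g = 10 to 30 | Type I error |
|---|---|---|
| 2% | 0.2-0.6 points | about 5% |
| 10% | 1-3 points | 6-13% |
| 20% | 2-6 points | 8-35% |

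The documents give neither g nor a definition of the per-protocol set. Both are assumptions here.

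**The case against.** The strongest reply is that nothing goes wrong if VAT already covers probe size. Section 2.4 introduces its list as examples, and it uses ablative treatment to mean either method. Section 2.5.1 is background, and no study-outline section cites it. Section 3.8 puts VAT before randomisation and describes LLETZ as part of the route for women who are not randomised. Section 3.9.1 assumes a single 20% ineligibility rate in each arm. On that reading the extra criterion operates before allocation and no asymmetry arises.

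Part of this stands: diversion after allocation is an inference, and the protocol nowhere orders it. It does not remove the inconsistency. Section 2.4 is background too, yet section 3.2.1 makes it operative, and its closing sentence treats every remaining case as amenable. The formal criteria in section 4.1 contain no lesion criteria, so section 2 is the only place where ablation eligibility is defined. If the list is open, different nurses may apply different gates before opening the card.

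A reader might go further and infer that both analyses are biased towards cryotherapy by several points. For example, crediting the 82% LLETZ figure (100 − 18) to lesions assumed only 50% curable by ablation gives 20% × 32 = 6.4 points in intention-to-treat at f = 20%. The documents do not support this. The cited trial shows a 9-point difference, not 32. Neither f nor the cure rate in large lesions is given. Intention-to-treat also preserves the randomised groups, so its problem would be contamination and not selection bias.

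**Conclusion.** Sections 2.4 and 2.5.1 do not agree on who may receive cryotherapy. As written, the mismatch allows an exclusion that acts in one arm after randomisation. Whether it would act depends on how the sites read the two sections.

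If it does act, the distortion can favour cryotherapy in both planned analyses. Its size depends on f: negligible near 2%, about 1 point in intention-to-treat and 1-3 points per-protocol at 10%, and about 2 and 2-6 points at 20%, in a trial sized for 10 points. These figures rest on the assumed f, on carrying the 9-point LLETZ difference over to large lesions, on the assumed 10-30 point deficit, and on a per-protocol set that drops diverted women.

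The documents do not establish that the cure-rate comparison is biased, only that the text leaves that possibility open. It is a should-fix and not a must-fix: the effect may be small, but a one-sided exclusion after allocation cannot be fully repaired in the analysis, and the correction is simple.

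**What to change.** Reconcile sections 2.4 and 2.5.1 into a single eligibility assessment that applies to both methods, and refer to it in section 3.8 (Module 2) and section 3.2.1 (Module 1 sub-arms A and B in South Africa). Require it to be completed and recorded before the A/B card is opened, and state that no method-specific exclusion applies after allocation. Record any later change of method, with its reason, by allocated arm. Which limits the assessment contains is for the clinical team.

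The cost is protocol wording and one checklist. The share found ineligible before randomisation may also rise, depending on the limits chosen and on f. If all women in the share f became ineligible, keeping the same number randomised would need 920/(1 − f) cases: about 939, 1,022 or 1,150 at f = 2%, 10% or 20%. The VAT records from the first enrolled women would show which end of that range applies.
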